3.9. STUDY HALTING RULES

Any SAE will serve as a stopping rule. The DSMB will convene to adjudicate the event. Enrollment will resume if the SAE is adjudicated by the DSMB. Additionally, if the SAE rate rises above 30% for two consecutive batches (10 cases per batch), the study will be halted.

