3.8. SAFETY OVERSIGHT

Safety oversight will be under the direction of a DSMB composed of individuals with the appropriate expertise, including interventional pulmonology. Out of an abundance of caution, the DSMB will meet to review cases and assess safety after each 10 consecutive patients have been enrolled (cases will be consecutively batched in groups of 10). The DSMB will operate under the rules of an approved charter that will be written and reviewed at the organizational meeting of the DSMB. At this time, each data element that the DSMB needs to assess will be clearly defined.

Proposed DSMB members:

[name]: DSMB Chair, Pulmonary and Critical Care, Medical University of South Carolina

[name]: Interventional Pulmonary, Duke University

[name], Division Chief, Pulmonary and Critical Care, Johns Hopkins University

[name], Interventional Pulmonary, University of Pittsburgh

[name], Pulmonary and Critical Care, University of Pennsylvania

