5.4.2. ANALYSIS OF THE PRIMARY SAFETY ENDPOINT

The primary endpoint is the incidence of serious adverse events defined as occurrence of bleeding grade ≥ 3 (see Adverse Events for bleeding grading system), pneumothorax requiring chest tube placement (Grade ≥ 2 , see Adverse Events for pneumothorax grading system), post-procedure respiratory failure defined as the need for non-invasive or mechanical ventilation requiring ICU admission, or death, which have occurred within 30 days after procedure, respectively. The incidence will be calculated as the proportion of patients in whom a serious adverse event occurred divided by those who underwent the index procedure (insertion of the cryoprobe into the working channel of the bronchoscope).

As the true safety profile of the 1.1mm flexible cryoprobe with oversheath is not currently known, and no standard minimally significant difference in a combined bleeding and pneumothorax outcome (such as in this study) is known, we will use currently available literature on a comparable biopsy method, (forceps biopsy and the larger 1.9mm and 2.4mm cryoprobes).

Based on review of the published literature (**Table 1**), we conservatively estimate the current combined bleeding and pneumothorax proportion to be 30% for transbronchial biopsy in standard practice. The procedure will be considered safe if the final proportion of serious adverse events is 30% or less. This will infer a standard of safety for the 1.1mm flexible single-use cryoprobe with oversheath comparable to current transbronchial biopsy standard of care.

Table 1: Literature review of bleeding and pneumothorax rates

Author	Definition of bleeding as per study	Number of patients in CBx, n (%)	Number of patients in FBx, n (%)
Aktas et al. (2010) ¹³ , (n = 41); All performed CB and FB; CB = 41, FB = 41	No bleeding Simultaneous bleeding Mild: cold water + adrenaline Moderate: APC application Severe : hemodynamic compromise Pneumothorax	26 (63.4) 5 (12.2) 8 (19.5) 2 (4.9) 0 (0) not reported	27 (65.9) 5 (12.2) 9 (21.9) 0 (0) 0 (0) not reported
Hetzell et al. (2012) ¹⁴ , (n = 593); CB = 296, FB = 297	No bleeding Mild: suctioning Severe: ice cold saline, diluted vasoconstrictive drug, balloon tamponade, APC, MV, conversion to rigid bronchoscope. Pneumothorax	59 (19.9) 183 (61.8) 54 (18.2) not reported	91 (30.6) 153 (51.5) 53 (17.8) not reported

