5.5. PLANNED INTERIM ANALYSES

Out of an abundance of caution for safety, following each 10 consecutively completed cases, the serious adverse event rate will be calculated. This data will only be available to the DSMB for review.

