5.6. SAFETY REVIEW

After any serious adverse event, a safety review will take place and recruitment at all sites will be halted. The DSMB will meet to review the case and overall safety of the trial, once adjudicated by the DSMB, the trial can be resumed.

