5.7. SAMPLE SIZE

This is a safety study. The goal of this study is to identify any high frequency adverse events, as well as collect preliminary data on the potential efficacy of the novel 1.1mm flexible single-use cryoprobe with oversheath. As no current data exists to accurately estimate the variance in SAE rates, there is no reliable data to power this study. We conservatively estimate that a stable estimation will of the SAE rate will occur after 50 cases. Thus in this initial study, we will include 50 participants.

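### The halting rule in 3.9 sets no cumulative limit, so enrollment can continue after the 30% criterion in 5.4.2 is out of reach

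*Combined protocol and SAP*

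**What the plan says.** All references are to the combined protocol and SAP. Section 3.9 has two rules.

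- **A pause at each event.** "Any SAE will serve as a stopping rule", followed by "Enrollment will resume if the SAE is adjudicated by the DSMB". Section 5.6 adds that after each SAE "The DSMB will meet to review the case and overall safety of the trial". It then permits the trial to restart once the event is adjudicated; it does not say that it will.
- **A numerical halt.** "if the SAE rate rises above 30% for two consecutive batches (10 cases per batch), the study will be halted".

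On batches, 3.8 says "cases will be consecutively batched in groups of 10", and 5.5 says "following each 10 consecutively completed cases, the serious adverse event rate will be calculated" without stating whether that rate is for the batch or cumulative. Section 5.7 fixes the size: "Thus in this initial study, we will include 50 participants". The decision rule is in 5.4.2: "The procedure will be considered safe if the final proportion of serious adverse events is 30% or less".

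No section sets a limit on the cumulative number of patients with an SAE, gives operating characteristics for the halting rule, or links that rule to the criterion in 5.4.2. The DSMB charter is still to be written (3.8).

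**The concern.** The final decision rests on the total over all patients, while the numerical halt looks only at two adjacent batches of 10. The two can part in either direction.

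- **Missed.** Batches of 5, 3, 5, 3 give 16 of 40. The trial can no longer end at 15 of 50 or fewer, no two adjacent batches exceed 30%, and ten more patients can be treated.
- **Halted although on course.** Batches of 0, 0, 4, 4 trigger the rule at 8 of 40 (20%). With 7 or fewer events in the last batch, the trial would have met 5.4.2.

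The first direction matters more. In a study whose primary endpoint is safety, patients can go on being exposed after the plan's own safety criterion is lost, and no written limit tells the DSMB that this point has passed.

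**Working it through.** **Inputs.** Five separate batches of 10 (3.8, 5.5, 5.7). Batch trigger: above 30% of 10, so at least 4. Final criterion: 0.30 × 50 = 15, so at most 15. The plan states no error rates, no operating characteristics and no true SAE rate, so there is no figure of its own to reproduce. The true rate p is assumed, over a range.

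**Step 1: chance of triggering.** Let a = P(X ≥ 4), X ~ Binomial(10, p). The rule is never triggered if no two adjacent batches are high. Counting the patterns of five batches with 0, 1, 2 or 3 non-adjacent high ones:

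P(no trigger) = (1−a)⁵ + 5a(1−a)⁴ + 6a²(1−a)³ + a³(1−a)²

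At p = 0.30, a = 0.3504, and the sum is 0.1157 + 0.3120 + 0.2019 + 0.0182 = 0.648. So P(trigger) = 0.352.

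**Step 2: joint with the final total.** All 11⁵ = 161,051 patterns of batch counts were enumerated with exact binomial weights.

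| True rate | P(batch ≥ 4/10) | P(trigger) | P(total > 15/50) | P(total > 15, no trigger) | P(trigger before patient 50, total ≤ 15) |
|---|---|---|---|---|---|
| 20% | 0.1209 | 0.0530 | 0.0308 | 0.0148 | 0.0278 |
| 25% | 0.2241 | 0.1652 | 0.1631 | 0.0700 | 0.0543 |
| 30% | 0.3504 | 0.3522 | 0.4308 | 0.1550 | 0.0577 |
| 35% | 0.4862 | 0.5720 | 0.7199 | 0.1963 | 0.0366 |
| 40% | 0.6177 | 0.7635 | 0.9045 | 0.1602 | 0.0145 |
| 50% | 0.8281 | 0.9586 | 0.9967 | 0.0389 | 0.0006 |

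As a share of the trials that fail 5.4.2, those missed are 0.1550/0.4308 = 36% at true 30%, 0.1963/0.7199 = 27% at 35%, 0.1602/0.9045 = 18% at 40% and 0.0389/0.9967 = 4% at 50%.

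In the last column, triggers at patient 50 are left out because no enrollment remains to halt. Including them gives 3.7% at true 20% and 7.7% at true 30%.

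**Step 3: the other reading.** Suppose the rate means the cumulative rate above 30% at two consecutive looks. The largest total that escapes a halt falls from 36 (10, 3, 10, 3, 10) to 22 (6, 0, 6, 0, 10). The missed probability becomes 0.0557, 0.0602, 0.0393 and 0.0043 at true 30%, 35%, 40% and 50%.

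**Step 4: adding a halt at the 16th patient with an SAE.** Every trial that ends above 15 contains a 16th such patient, so the missed probability becomes zero under either reading. A trial that ends at 15 or fewer never reaches one, so no halt of a passing trial is added. On the per-batch reading, mean patients treated change as follows:

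- True 30%: 43.9 to 43.0, a saving of 0.9.
- True 40%: 34.2 to 32.2, a saving of 2.0.
- True 50%: 25.9 to 24.5, a saving of 1.4.

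**The case against.** The strongest reply is that the batch rule does not stand alone. The study pauses at the first SAE, the DSMB reviews overall safety after each one (5.6), and it meets after every 10 patients (3.8). A board that sees 16 events can act. That stands, and it rules out several stronger readings.

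- **That nothing can happen before patient 20.** This is true only of the numerical rule. The per-event pause acts from the first SAE.
- **That 36 of 50 patients could realistically have an SAE unhalted.** The pattern is possible, but its probability is about 2 in a billion even at the true rate that favors it most (72%). Finishing unhalted with 25 or more has probability of at most about 0.2% at true rates from 10% to 60%. Missed trials are mostly marginal: the median total is 17 at true 30% and 18 at true 40%.
- **That the DSMB must let the trial resume whatever it concludes.** No section says so. Section 3.9 makes resumption conditional on adjudication, and 5.6 is permissive.
- **That halting at 8 of 40 contradicts 5.4.2.** A halt is not a finding that the procedure is unsafe, and two poor batches in a row can reasonably prompt one. The documents nowhere require the two rules to match.

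A sponsor could add that 5.1 disclaims power for a statistical conclusion. That does not settle the matter, because 3.9 and 5.4.2 still set numerical decisions. Nor does the pause close the gap: it carries no limit, and adjudicating an event is not the same as recommending that the trial continue.

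**Conclusion.** The concern holds as a missing cumulative limit, together with loose resumption wording. On the per-batch reading, 16% to 20% of trials at true rates of 30% to 40%, and 4% at 50%, end above 15 of 50 without triggering the only numerical rule. On the cumulative reading the figures are about 4% to 6% at true 30% to 40%. Early halts of trials that would have passed are less frequent: 2.8% at true 20% and 5.8% at true 30%.

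The figures assume independent patients with a constant SAE rate, 50 patients in the denominator of 5.4.2, and batch counts complete at review. The last may fail: 3.8 counts enrolled patients, 5.5 counts completed cases, and events accrue over 30 days. The figures describe the numerical rule alone, because the DSMB's judgment at each pause cannot be modeled from the documents.

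**What to change.** Keep the two-batch rule and make three edits, in 3.9, 5.6 and the DSMB charter.

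1. State whether the rate in the two-batch rule is per batch or cumulative.
2. Add: *Enrollment will also be halted when the 16th patient has a primary-endpoint SAE, because the criterion in 5.4.2 can then no longer be met.*
3. Reconcile the resumption wording of 3.9 and 5.6, so that enrollment resumes only if the DSMB recommends it after its overall safety review.

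The cost is a few sentences. Trials that fail the criterion stop with fewer than 50 patients, so their SAE rate and secondary descriptive data are slightly less precise.

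Replacing the two-batch rule with cumulative boundaries of 6/10, 10/20 and 14/30 (smallest counts with exact one-sided p ≤ 0.05 against 30%), plus the 16th-patient halt, is an optional design choice and not a free gain. Compared with the rule as written:

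- It halts fewer passing trials before patient 50: 0.5% against 2.8% at true 20%, and 1.0% against 5.8% at true 30%.
- It treats fewer patients on average at high rates: 22.0 against 25.9 at true 50%, and 15.0 against 21.7 at true 60%.
- It stops fewer trials by patients 20 and 30 at true rates of 30% to 50%. At true 40% the figures are 30% against 38% by patient 20, and 38% against 53% by patient 30.
- It treats more patients on average at true 30%: 45.1 against 43.9.

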4. CLINICAL MONITORING

Clinical site monitoring is conducted to ensure that the rights and well-being of human subjects are protected, that the reported trial data are accurate, complete, and verifiable, and that the conduct of the trial is in compliance with the currently approved protocol/amendment(s), with GCP, and with applicable regulatory requirement(s).

- Monitoring for this study will be performed by Johns Hopkins University
- Centralized, initial assessments and monthly assessments, and comprehensive review of all primary and secondary endpoint data.

- Details of clinical site monitoring are documented in a CMP. The CMP describes in detail who will conduct the monitoring, at what frequency monitoring will be done, at what level of detail monitoring will be performed, and the distribution of monitoring reports.
- Independent audits will be conducted by Johns Hopkins University to ensure monitoring practices are performed consistently across all participating sites and that monitors are following the CMP.

5. STATISTICAL CONSIDERATIONS

5.1. STATISTICAL AND ANALYTICAL PLANS

The study is not powered to make a statistical conclusion due to the small sample size and the safety phase in which the treatment is. As the true safety profile of the 1.1mm flexible single-use cryoprobe with oversheath is not known, we will base our statistical plan based on current standard method for transbronchial biopsy, forceps biopsy.

5.2. STATISTICAL HYPOTHESES

1. To determine the serious adverse event rate of a 1.1mm flexible single-use cryoprobe with oversheath for transbronchial bronchoscopic biopsy.

We hypothesize that the serious adverse event proportion using the novel smaller, 1.1mm flexible single-use cryoprobe with oversheath will not exceed 30%, the adverse event proportion for the current standard method of transbronchial biopsy using forceps.

2. To determine baseline performance characteristics for the use of the 1.1mm flexible single-use cryoprobe with oversheath.

We hypothesize that data generated during the performance of this safety trial will generate meaningful descriptive statistics for pathologic evaluation (histologic adequacy), procedural characteristics (activation time, number of biopsies taken, type of airway used), and diagnostic yield across various disease states necessitating transbronchial biopsy. This descriptive data will be crucial in the planning of future clinical trials.

5.3. ANALYSIS DATASETS

All analyses will be done using intention-to-treat analyses to properly identify safety and baseline performance characteristics. As participants will not be randomized, the index action for inclusion will be insertion of the cryoprobe into the working channel of the bronchoscope.

5.4. DESCRIPTION OF STATISTICAL METHODS

5.4.1. GENERAL APPROACH

This is a multi-centered, prospective, single arm trial aimed at establishing the safety profile of a novel 1.1mm flexible single-use cryoprobe with oversheath. Secondary outcomes will be descriptive procedural characteristics that will be used to power future trials.

All continuous data will be presented as means with standard deviations. Categorical data will be represented by percentages. Statistical comparisons will be made using linear and logistic regression

analysis where applicable. Sensitivity, specificity, positive and negative predictive value and accuracy of all procedures will be calculated.

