be placed in saline. The removal tool accompanying each cryoprobe can be used to carefully remove the specimen from the tip of the cryoprobe only after the specimen was defrosted. Specimens will then be transferred into a fixative (i.e. formalin) per institutional policy and sent to the local institutional pathology lab for processing and interpretation. Each biopsy sample will then be sent for central pathology interpretation. If tissue cultures are clinically indicated, an additional specimen may be placed in sterile saline

For non-lung transplant rejection related biopsies, a minimum of 3 biopsies must be taken using the 1.1mm sheath cryoprobe. For lung transplant rejection surveillance biopsies, a minimum of 5 cryobiopsies must be taken (more if needed), as per IHS LT guidelines, at least 5 pieces of well-expanded alveolated lung parenchyma are required for an assessment of acute rejection.⁹ As part of this study, only cryobiopsy with the 1.1mm single-use flexible cryoprobe with oversheath is permitted for transbronchial lung biopsy. This excludes the use of needle, forceps, and brush biopsy. In case of cryoprobe failure a new 1.1mm sheath cryoprobe should be used. A bronchoalveolar lavage or wash is allowed if clinically indicated but must be performed after the index procedure is performed.

Following the procedure, the patient will be returned to the post-anesthesia care unit and a post-procedural chest x-ray will be obtained and results will be documented.

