3.6. DATA COLLECTION

Collected data include: radiographic characteristics, procedural characteristics, diagnostic yield, and adverse events, as follows:

- *Radiographic Characteristics:*

If a target location is present (i.e. biopsy for lung nodule), the location of the target lesion (side, lobe and segment, i.e. right upper lobe anterior segment, etc.) will be determined and recorded. The radiographic information collected will include size of the lesion (longest axis), distance from a visible bronchus, and distance from the pleural surface perpendicular to the lesion on axial cuts. If the patient has undergone a PET scan, the metabolic activity (measured SUV) will be recorded.

If target lesions exists, to assess centrality, we will utilize proprietary software to map zones of the lung to determine if a lesion falls into the outer, middle, or central 1/3 of the lung parenchyma. "CT Pulmo 3D" workflow using Siemens Syngo via software automatically analyzes the lung parenchyma and define the contours of both lungs (Figure 1). This will be performed by the core radiology laboratory at Johns Hopkins. External sites to Johns Hopkins (Vanderbilt University) will submit the de-identified CT scan via a secure program (Ambra) that is in clinical use for secure image sharing.

[figure not shown]

Figure 2: CT Pulmo 3D software output defining central, middle and peripheral lung zones¹⁰

For diffuse lung disease, the CT characteristic pattern will be recorded (i.e. UIP, NSIP, cystic, reticular nodular). Additionally, localization and distribution of infiltrates will be collected. If no specific lung abnormalities are noted on CT (i.e. lung transplant surveillance), this will be recorded.

- **Procedural Characteristics:**

Collected procedural information will include the number of biopsy attempts, freeze time for each biopsy, procedural time (scope in to scope out) and use of prophylactic bronchial blocker. The type (general or moderate) of sedation administered as well as artificial airway selection (ETT, LMA, rigid bronchoscopy) will also be recorded. Room temperature and gas pressure, number of probes used.

- **Pathology Core Lab Assessment:**

An independent pathology core lab will review all study cases. The core lab will be graded on a previously validated histologic accessibility on a 7-point Likert Scale^{6,11} as follows:

- Grade 0: The specimen does not contain alveolar structures and can therefore not be assessed as transbronchial biopsy specimen

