- Grade 1: Due to very poor specimen quality, it is not possible to assess the relevant morphologic and histologic features
- Grade 2: Due to poor specimen quality, assessment of relevant morphologic and histologic structures and features is severely compromised and not possible
- Grade 3: Despite high limitations in specimen quality, assessment of the relevant morphologic and histologic structures and features is severely compromised but possible
- Grade 4: Despite moderate limitations in specimen quality, assessment of the relevant morphologic and histologic structures and features is compromised but possible
- Grade 5: Despite low limitations in specimen quality, assessment of the relevant morphologic and histologic structures and features are compromised but possible

- Grade 6: The specimen allows for complete and unrestricted assessment of all relevant morphologic and histologic structures and features

Additionally, the pathologic core lab will determine, the total histologic area (mm²), alveolated area (mm²), open alveoli percent, percent crush artifact, and artifact free lung parenchyma percent. The underlying diagnosis will be confirmed or rebutted.

▪ *Diagnostic Yield:*

Diagnostic yield is defined as proportion of patients for which cryobiopsy led to a diagnosis. Diagnostic yield will be determined from the results of cryobiopsy specimen only. A biopsy that results in a specific diagnosis, either malignant or benign (granuloma, inflammation, fibrosis, infection) will be assumed to be a true positive. Atypia, minimal inflammation or lung parenchyma without pathologic findings on final pathology reads are considered non-diagnostic.

▪ *Room Temperature and Gas Pressure:*

The room temperature of the OR (by a thermometer fixed to the ERBECRYO 2 unit) and the gas pressure which is displayed on the cryo unit will be collected prior to the index procedure. This ensures standardized results throughout the study. The gas pressure and the room temperature must be at least 56bar and 68°F (20°C), respectively.

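### Section 5.4.1 promises sensitivity, specificity, predictive values and accuracy, but the plan has no target condition or reference standard from which to calculate them

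*Combined protocol and SAP*

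**What the plan says.** The commitment in section 5.4.1 carries no condition: "Sensitivity, specificity, positive and negative predictive value and accuracy of all procedures will be calculated". The sentence before it, on regression, is limited to cases where the method applies; this one is not.

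The only rules for classifying a biopsy result are those for diagnostic yield in section 3.6. They use the study biopsy alone: "Diagnostic yield will be determined from the results of cryobiopsy specimen only". A specific malignant or benign diagnosis "will be assumed to be a true positive". On the other side, "Atypia, minimal inflammation or lung parenchyma without pathologic findings on final pathology reads are considered non-diagnostic". Section 5.4.3 repeats the true-positive assumption, but not the list of non-diagnostic results, and analyses yield as a simple proportion of patients.

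On central review, section 3.4 says "Each biopsy sample will then be sent for central pathology interpretation", and section 3.6 says of the core lab's work: "The underlying diagnosis will be confirmed or rebutted". Section 3.4 allows only the study cryoprobe for transbronchial lung biopsy: "This excludes the use of needle, forceps, and brush biopsy".

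The five accuracy measures appear neither among the secondary endpoints in section 2.3 nor among the secondary analyses in section 5.4.3.

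**The concern.** Each of the five measures needs three things: a condition that the test is meant to detect, a reference standard that establishes the patient's true state independently of the test, and a rule that puts every result in one cell of a 2x2 table. The plan supplies at most part of the third. The population also mixes indications (section 2.1 lists transplant surveillance, nodules, diffuse parenchymal disease and pneumonitis), so there is no single obvious target. Lung tissue without pathologic findings is non-diagnostic under section 3.6, yet in a surveillance patient it could be a correct negative if rejection were the target.

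At stake is a set of figures that would look like test accuracy but would be fixed by definitions chosen at the time of analysis. Section 5.2 says that the descriptive results are meant to inform the planning of later trials, so such figures could be carried forward.

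**Working it through.** The plan gives no value, precision target or sample-size argument for any accuracy measure, so there is no figure of its own to reproduce. The check has three parts.

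**1. Could any planned data serve as the reference standard?**
- Data list. Section 3.6 opens with "Collected data include: radiographic characteristics, procedural characteristics, diagnostic yield, and adverse events, as follows". The items that follow are imaging features, procedural details, core-lab grading, yield, and room temperature and gas pressure. A final diagnosis reached independently of the biopsy is not among them.
- Core lab. It reads the study specimens. A second read of the same tissue measures agreement between readers. It cannot show disease in tissue that was not sampled, so it cannot establish false negatives.
- Other sampling. Lavage (section 3.4) and convex EBUS (section 3.5) are allowed, but neither is called a reference and neither is required in every patient.
- Follow-up. The 30-day follow-up in section 3.7.6 is described for adverse events.

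None of these fills the gap.

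**2. What follows if the yield rule is reused?** This is an assumption; the documents do not say that it will be. Let N be the number of patients, x the number with a specific diagnosis, and N − x the number with a non-diagnostic read, split into FN and TN. All x are true positives, so FP = 0 and:
- PPV = x/(x + 0) = 100% for any x > 0
- Specificity = TN/(TN + 0) = 100%, or 0/0 if TN = 0
- Sensitivity = x/(x + FN)
- Accuracy = (x + TN)/N
- NPV = TN/(N − x)

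The last three depend on the split of non-diagnostic reads, which the plan does not give.

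**3. Numbers.** N = 50 is from section 5.7, with all 50 taken as analysed. The yields of 58% (x = 29) and 34% (x = 17) are the two ends of the forceps range for diffuse lung disease in section 1, used only as assumed values.

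| Assumed x | Non-diagnostic reads | Sensitivity | Accuracy | NPV | Specificity | PPV |
|---|---|---|---|---|---|---|
| 29 | all 21 FN | 29/50 = 58.0% | 29/50 = 58.0% | 0/21 = 0% | 0/0 | 29/29 = 100% |
| 29 | all 21 TN | 29/29 = 100% | 50/50 = 100% | 21/21 = 100% | 21/21 = 100% | 29/29 = 100% |
| 17 | all 33 FN | 17/50 = 34.0% | 17/50 = 34.0% | 0/33 = 0% | 0/0 | 17/17 = 100% |
| 17 | all 33 TN | 17/17 = 100% | 50/50 = 100% | 33/33 = 100% | 33/33 = 100% | 17/17 = 100% |

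Yield itself needs no 2x2 table. Its exact (Clopper-Pearson) 95% confidence interval would be 43.2% to 71.8% at 29/50 and 21.2% to 48.8% at 17/50.

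**The case against.** The strongest reply is that the sentence sits in a general paragraph of a study that section 5.1 describes as not powered for a statistical conclusion, and that section 3.6 does define both diagnostic and non-diagnostic results. The first part stands and limits the severity. The second does not answer the point, because those definitions serve yield: they do not say whether a non-diagnostic read is a missed case or a correct negative.

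Five stronger readings are tempting, and the documents do not support them.
- A reader might infer that PPV must come out at 100%. That holds only if the yield rule is reused. The core lab may rebut a diagnosis, and counting rebuttals as false positives would lower the figure, although the result would then be reader agreement rather than predictive value.
- A reader might treat the ranges in the table as likely results. They are bounds. The upper end requires every non-diagnostic read, including atypia, to be free of the target condition.
- A reader might add a third option in which non-diagnostic reads are dropped. At x = 29, sensitivity and accuracy would then be 29/29 = 100%, with specificity and NPV 0/0. Section 5.3 applies intention-to-treat to all analyses, with inclusion set by probe insertion. It does not assign reads to cells, but it sits poorly with dropping patients for an inconclusive result.
- A reader might find the scope of the sentence in 5.4.1 undefined. With a single transbronchial biopsy tool allowed, it most naturally covers all study cryobiopsies.
- A reader might conclude that yield is free of classification choices. It is not: it depends on the section 3.6 line between diagnostic and non-diagnostic results, including the line between inflammation and minimal inflammation.

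**Conclusion.** The point holds, at minor severity. Section 5.4.1 commits to an analysis that the design cannot support, and an analyst could not repair this from the planned data. That conclusion rests on what sections 3.4, 3.5, 3.6 and 3.7.6 provide for, and does not depend on the assumed yields. The numerical bounds do depend on the reuse of the yield rule and on the assumed values of x; they show only that the plan leaves the measures undetermined.

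A reader might infer that the trial's safety conclusion or its yield result is compromised. The documents do not support that. No decision rule uses the accuracy measures, the primary endpoint in section 5.4.2 does not involve them, and yield is calculated as before.

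**What to change.** Delete the sentence from section 5.4.1. State in its place that diagnostic yield, under the section 3.6 definition, is the only measure of diagnostic performance, preferably reported with an exact (Clopper-Pearson) 95% confidence interval. The interval is a reporting improvement; the deletion is what resolves the problem. For consistency, in sections 3.6 and 5.4.3 replace "will be assumed to be a true positive" with *will be counted as diagnostic*. If the percentage of diagnoses confirmed by the core lab is reported, label it as agreement between readers.

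If the sponsor wants accuracy after all, the plan would have to name, for each indication, the target condition, an independent reference standard and the 2x2 placement of non-diagnostic reads. That needs data not on the section 3.6 list.

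The preferred change needs no new data. It costs a small wording amendment, with sponsor agreement under the Statement of Compliance and local IRB approval under section 9.2, and the loss of accuracy figures that the planned data could not support.
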